6.3 Study Product Formulation and Storage

Inserts will be packaged in 20 cc, round, white, high-density polyethylene (HDPE) bottles with a child-resistant closure and aluminum, induction-sealed foil liner. Each bottle will contain 20 vaginal inserts and be labeled as per local requirements. Study product will be dispensed for the number of inserts needed for each phase.

Study products should be stored in white induction-sealed HDPE bottle along with polyester coil and a desiccant at room temperature (15° - 30°C) (59° - 86°F) in a locked cabinet or secure area in the clinic prior to dispensing. Consideration should always be given to measures that minimize contact during handling, preparation, and disposal procedures.

6.3.1 TAF/EVG Vaginal Insert

The product being used in this study is the TAF/EVG Vaginal Insert 20/16 mg. Each insert for vaginal administration contains 20 mg tenofovir alafenamide (TAF) and 16 mg elvitegravir (EVG). TAF is a nucleotide reverse transcriptase inhibitor (NRTI) and a prodrug of tenofovir and EVG is an integrase inhibitor. Both of the active pharmaceutical ingredients (APIs) are supplied by Gilead Sciences, Inc.

In addition to the APIs, the insert contains the following inactive excipients: Povidone, magnesium stearate, Polaxomer (also known as Kolliphor), polyethylene glycol, mannitol, and lactose anhydrous. The insert dimensions are: length: 1.5 cm, width: 0.7 cm, height: 0.6 cm. Each insert is approximately 500 mg in weight. The insert formulation is manufactured under current Good Manufacturing Practice (cGMP) at Patheon Pharma Services (part of Thermo Fisher Scientific), Whitby, ON, Canada.

6.3.2 Matching Placebo Vaginal Insert

The placebo vaginal insert will be similar in appearance to the TAF/EVG insert. The composition of the insert includes: lactose anhydrous, mannitol, polyethylene glycol, Povidone, Polaxomer (also known as Kolliphor), and magnesium stearate. The insert dimensions are: length: 1.5 cm, width: 0.7 cm, height: 0.6 cm. Each insert is approximately 500 mg in weight. The insert formulation is manufactured under current Good Manufacturing Practice (cGMP) at Patheon Pharma Services (part of Thermo Fisher Scientific), Whitby, ON, Canada.

6.4 Supply and Accountability

CONRAD will oversee the manufacture and analysis/release (Patheon Pharma Services (part of Thermo Fisher Scientific), Whitby, ON, Canada) of the study product under current Good Manufacturing Practices (cGMP).

6.4.1 Study Product Supply

The site will manage the distribution of the study product according to the protocol. The site will be provided sufficient study product for its designated number of participants. Supplies will be distributed by CONRAD or CONRAD designee.

6.4.2 Study Product Dispensing

TAF/EVG Inserts will be dispensed to clinic staff on behalf of the participant or directly to the participant, upon receipt of a written prescription from an authorized prescriber. An authorized prescriber includes the IoR or a licensed clinician(s) directly responsible to the IoR as noted on the Form FDA 1572.

6.4.3 Study Product Accountability

Each Clinical Research Site (CRS) Pharmacist of Record (PoR) is required to maintain a complete record of all TAF/EVG inserts received and subsequently dispensed. All unused TAF/EVG inserts

must be returned to the IND Sponsor, CONRAD, after the study is completed or terminated unless otherwise instructed by the IND Sponsor.

6.4.4 Retrieval of Unused Study Products

All undispensed study product remaining at the end of the study will be recorded by the site and reconciled by the study monitor(s). After reconciliation, the sponsor will provide instruction regarding disposal, storage, or return of product.

6.5 Ancillary Study Supplies

Clinic staff will offer male condoms to all participants.

6.6 Concomitant Medications

All concomitant medications will be recorded on CRFs for participants starting at Screening. Participants may use acetaminophen (paracetamol) on an as-needed basis during the study. Concomitant medications include all prescription medications, over-the-counter preparations, vitamins, nutritional supplements, recreational drugs, and herbal preparations.

6.7 Prohibited Medications, Products and Practices

6.7.1 Prohibited Medications and Products

Participants should not use the prohibited medications and products as listed in Appendix III during the study unless instructed by a clinician in which case they should inform study staff.

6.7.2 Prohibited Practices

Participants will be asked to abstain from any vaginal and anal activity, douching, and use of all intravaginal objects and products at the times specified below.

- Beginning 48 hours before enrollment visit, during daily dosing phase and approximately 48 hours before and 10 days after CVT biopsy collections:
 - Vaginal and/or anal intercourse
 - Finger stimulation
 - Insertion of fingers or any objects into the vagina or rectum including
 - Sex toys, female condoms, diaphragms, or other vaginal barrier methods
 - Menstrual cups and tampons (acceptable to use outside of dosing phases)
- 72 hours before and after CVT biopsy collections:
 - Use of aspirin greater than 81 mg
- For the duration of the study:
 - Use of any drugs which could prolong bleeding and/or clotting or otherwise interfere with study results per study criteria (i.e., daily NSAID use, St. John's Wort, blood thinners, etc.)
 - Use of vaginal products including spermicides, lubricants, douches, medications, moisturizers, or contraceptive vaginal rings

7 STUDY PROCEDURES

An overview of the study visits and evaluations schedule is provided in Appendix I. Presented in this section is additional information on visit-specific study procedures. Detailed instructions to guide and standardize procedures across sites as well as to specify the visit windows are provided in the MATRIX-001 SSP Manual.

Figure 3: Study Visit Schedule

See Figure 1: Study Visit Schedule.

7.1 Screening Visit

Potential participants will provide written informed consent for screening and enrollment prior to any study related procedures. Eligibility determination will start at Visit 1 and be confirmed in Visit 2. This will include baseline medical history, physical and pelvic examinations, urine pregnancy test (UPT), HIV/STI screening, and blood baseline safety tests at Visit 1. Menstruating participants will be scheduled after menstrual flow ceases and ideally in the luteal phase of the menstrual cycle. Note that if the participant is not able to complete or needs to repeat any of the study procedures conducted at this visit (e.g., blood draw), she may return prior to Visit 2. Labs may be repeated during the screening window per IoR/designee discretion.

Note: Potential participants who fail their first screening attempt may be re-screened once.

Table 1: Screening Visit

Screening Visit – Visit 1		
Component		Procedures
Administrative and Regulatory		
 ● Informed consent process ● Assess eligibility ● Assign a unique Participant Identification (PTID) number ● Collect locator information ● Provide reimbursement ● Schedule next visit/contact, if indicated
Behavioral/Counseling		
 ● Protocol requirements counseling per Section 7.8 ● Pre- and post-test HIV counseling, and risk reduction counselling ● Collect demographic information
Clinical		
 ● Collect medical and menstrual history ● Assess concomitant medications (CM) ● Pelvic (with bimanual) exam ● Full physical exam ● Treat or prescribe treatment for reproductive tract infections (RTI)/ urinary tract infections (UTI)/STIs, if indicated ● Provide available test results
Laboratory	Urine	
 ○ Pregnancy test ○ Urine dipstick/urinalysis
	Blood	
 ○ HIV, HBsAg, HSV-2*, Syphilis, complete blood count (CBC) with platelets, Chemistries

Screening Visit – Visit 1		
Component		Procedures
	Genital	
 ○ TV, GC, CT testing ○ Pap smear, if indicated ○ Saline/potassium hydroxide (KOH) wet mount for candidiasis and/or bacterial vaginosis (BV), if indicated

*HSV-2 results will not be provided to participants

7.2 Baseline Visits

7.2.1 Enrollment Visit – Visit 2

The enrollment visit should be scheduled within 8 weeks of Screening/Visit 1. Willing and eligible participants will be asked to complete a baseline acceptability questionnaire, provide a urine sample for a UPT and undergo HIV screening, provide a blood sample for plasma archive, and undergo baseline sample collection of CVF for PD, CVT for subclinical safety and PD, and cervicovaginal lavage (CVL) collection. Willing and eligible participants will be scheduled after menstrual flow ceases and ideally in the luteal phase of the menstrual cycle.

Table 2: Enrollment Visit

Enrollment Visit – Visit 2		
Component		Procedures
Administrative and Regulatory		
 ● Confirm participation ● Confirm eligibility ● Review/update locator information ● Provide reimbursement ● Schedule next visit/contact, if indicated
Behavioral/Counseling		
 ● Naïve product use assessment ● Baseline behavioral questionnaire ● Protocol requirements/prohibited vaginal and anal activity ● Pre- and post-test HIV counseling, and risk reduction counselling
Clinical		
 ● Review/update medical and menstrual history ● Assess CM ● Pelvic exam ● Directed physical examination, if indicated ● Vital signs and weight ● Treat or prescribe treatment for RTI/UTI/STIs, if indicated ● Provide available test results
Laboratory	Urine	
 ○ Pregnancy test ○ Urine dipstick/urinalysis, if indicated
	Blood	
 ○ HIV ○ Plasma archive
	Genital	
 ○ PSA test for semen ○ Gram stain for Nugent score, pH ○ CVF for anti-HIV and anti-HSV ○ CVL for soluble markers ○ Vaginal biopsy (BXV) for immunohistochemistry (IHC) ○ Ectocervical biopsy (BXC) for HIV (EVMS only) ○ TV, GC, CT testing, if indicated ○ Saline/KOH wet mount for candidiasis and/or BV, if indicated

7.2.2 Randomization Visit – Visit 3

Visit 3 should be scheduled 10-14 days after Visit 2, not less than 10 days after biopsy. Visit 3 will be scheduled shortly after menstrual flow ceases for cycling participants to ensure the 3 days of product use do not occur during a menstrual cycle.

Participants will provide a urine sample for a UPT and undergo HIV screening prior to randomization. Participants will also complete a brief product use assessment and undergo baseline pre-insertion sample collection of CVL, CVF for PK, PD, and vaginal microbiota, and (if participant agrees) RF for PK. Provided they have negative HIV and pregnancy test results, participants will be randomized (1:1) to receive TAF/EVG versus placebo vaginal insert. Participants will also be randomized (1:1:1) into three time points for PK tissue sampling after the last dose (24, 48, or 72 hours post last dose).

Participants will then self-administer the first dose (single combination insert of TAF/EVG or placebo) in the clinic. Participant will be dispensed doses 2 and 3 for daily insertion at home.

Table 3: Randomization Visit

Randomization Visit – Visit 3		
Component		Procedures
Administrative and Regulatory		
 ● Confirm participation ● Conduct product assignment randomization (after HIV and pregnancy tests) ● Conduct PK tissue sampling randomization (after HIV and pregnancy tests) ● Review/update locator information ● Provide reimbursement ● Schedule next visit/contact
Behavioral/Counseling		
 ● Protocol requirements/prohibited vaginal and anal activity ● Pre- and post-test HIV counseling, and risk reduction counselling ● Initial product use assessment
Clinical		
 ● Review/update medical and menstrual history ● Assess adverse events (AE) and CM ● Pelvic exam pre-dosing ● Directed physical examination, if indicated ● Vital signs and weight ● Treat or prescribe treatment for RTI/UTI/STIs, if indicated ● Provide available test results
Laboratory	Urine	
 ○ Pregnancy test ○ Urine dipstick/urinalysis, if indicated
	Blood	
 ○ HIV
	Genital	
 ○ PSA test ○ Gram stain for Nugent score, pH ○ CVF for PK and PD ○ CVL for soluble markers ○ Vaginal microbiota ○ TV, GC, CT testing, if indicated ○ Saline/KOH wet mount for candidiasis and/or BV, if indicated
	Anorectal	
 ○ RF for PK (if participant agrees)

Randomization Visit – Visit 3	
Component	Procedures
Study Product/Supplies	
 • Self-insertion of 1st dose • Dispense doses 2-3 for home insertion

7.3 Follow-up Visits/Contacts

7.3.1 24-hour Post Third Dose Visit – Visit 4

Participants will undergo sample collection of CVL, blood for PK, CVF for PK, PD, and vaginal microbiota, CVT for PK and PD, (if participant agrees) RF for PK, and complete a brief product use assessment.

Table 4: 24-hour Post Third Dose Visit

24-hour Post Third Dose Visit – Visit 4		
Component	Procedures	
Administrative and Regulatory	
 • Confirm participation • Review/update locator information • Provide reimbursement • Schedule next visit/contact 	
Behavioral/Counseling	
 • Protocol requirements/prohibited vaginal and anal activity • Product use assessment 	
Clinical	
 • Review/update medical and menstrual history • Assess for AE and CM • Pelvic exam • Directed physical examination, if indicated • Vital signs and weight • Treat or prescribe treatment for RTI/UTI/STIs, if indicated • Provide available test results 	
Laboratory	Urine	
 ○ Pregnancy test, if indicated ○ Urine dipstick/urinalysis, if indicated
	Blood	
 ○ Plasma for PK
	Genital	
 ○ PSA test ○ Gram stain for Nugent score, pH ○ CVF for PK and PD ○ CVL for soluble markers ○ Vaginal microbiota ○ BXV for PK ○ BXC for HIV (EVMS only) ○ TV, GC, CT testing, if indicated ○ Saline/KOH wet mount for candidiasis and/or BV, if indicated
	Anorectal	
 ○ RF for PK (if participant agrees)

7.3.2 Fourth Dose Visit – Visit 5

Visit 5 should be scheduled 10-14 days after Visit 4, not less than 10 days after biopsy. Visit 5 will be scheduled shortly after menstrual flow ceases for cycling participants to ensure the 14 days of product use do not occur during a menstrual cycle.

Participants will undergo pre-insertion sample collection of CVL, blood for PK, CVF for PK, PD, and vaginal microbiota, and (if participant agrees) RF for PK. Participants will then self-administer the fourth dose at the clinic.

Table 5: Fourth Dose Visit

Fourth Dose Visit – Visit 5		
Component		Procedures
Administrative and Regulatory		
 ● Confirm participation ● Review/update locator information ● Provide reimbursement ● Schedule next visit/contact
Behavioral/Counseling		
 ● Protocol requirements/prohibited vaginal and anal activity
Clinical		
 ● Review/update medical and menstrual history ● Assess for AE and CM ● Pelvic exam pre-dosing ● Directed physical examination, if indicated ● Vital signs and weight ● Treat or prescribe treatment for RTI/UTI/STIs, if indicated ● Provide available test results
Laboratory	Urine	
 ○ Pregnancy test, if indicated ○ Urine dipstick/urinalysis, if indicated
	Blood	
 ○ Plasma for PK
	Genital	
 ○ PSA test ○ Gram stain for Nugent score, pH ○ CVF for PK and PD ○ CVL for soluble markers ○ Vaginal microbiota ○ TV, GC, CT testing, if indicated ○ Saline/KOH wet mount for candidiasis and/or BV, if indicated
	Anorectal	
 ○ RF for PK (if participant agrees)
Study Product/Supplies		
 ● Self-insertion of 4th dose

7.3.3 Fifth Dose Visit – Visit 6

Visit 6 will take place two days after Visit 5. Participants will undergo pre-insertion sample collection of CVL, blood for PK, CVF for PK, PD, and vaginal microbiota, and (if participant agrees) RF for PK. Participants will then self-administer the fifth dose at the clinic and receive their sixth to tenth doses for home insertion QOD.

Table 6: Fifth Dose Visit

Fifth Dose Visit – Visit 6		
Component		Procedures
Administrative and Regulatory		
 ● Confirm participation ● Review/update locator information ● Provide reimbursement ● Schedule next visit/contact
Behavioral/Counseling		
 ● Protocol requirements/prohibited vaginal and anal activity

Fifth Dose Visit – Visit 6		
Component	Procedures	
Clinical	
 ● Review/update medical and menstrual history ● Assess for AE and CM ● Pelvic exam pre-dosing ● Directed physical examination, if indicated ● Vital signs and weight ● Treat or prescribe treatment for RTI/UTI/STIs, if indicated ● Provide available test results 	
Laboratory	Urine	
 ○ Pregnancy test, if indicated ○ Urine dipstick/urinalysis, if indicated
	Blood	
 ○ Plasma for PK
	Genital	
 ○ PSA test ○ Gram stain for Nugent score, pH ○ CVF for PK and PD ○ CVL for soluble markers ○ Vaginal microbiota ○ TV, GC, CT testing, if indicated ○ Saline/KOH wet mount for candidiasis and/or BV, if indicated
	Anorectal	
 ○ RF for PK (if participant agrees)
Study Product/Supplies		
 ● Self-insertion of 5th dose ● Dispense doses for home insertion

7.3.4 24/48/72-hours Post Last Dose Visit – Visit 7

Visit 7 will take place either 11, 12 or 13 days after Visit 6. Visit 7 will be split into three timepoints: a) 24-hours post last dose, b) 48-hours post last dose, and c) 72-hours post last dose. Only a third of participants will attend each timepoint, depending on randomization at Visit 3. Participants will provide a urine sample for a UPT, a blood sample for safety tests, and undergo HIV/STI testing. Participants will also undergo sample collection of CVL, blood for PK, CVF for PK, PD, and vaginal microbiota, CVT for subclinical safety, PK and PD, (if participant agrees) RF for PK, and complete an acceptability questionnaire.

Table 7: 24/48/72-hours Post Last Dose Visit

24-hr/48-hr/72-hr Post Last Dose – Visit 7	
Component	Procedures
Administrative and Regulatory	
 ● Confirm participation ● Review/update locator information ● Provide reimbursement ● Schedule next visit/contact
Behavioral/Counseling	
 ● Comprehensive behavioral and product use questionnaire ● Protocol requirements/prohibited vaginal and anal activity ● Pre- and post-test HIV counseling, and risk reduction counselling
Clinical	
 ● Review/update medical and menstrual history ● Assess for AE and CM ● Pelvic exam ● Directed physical examination, if indicated ● Vital signs and weight ● Treat or prescribe treatment for RTI/UTI/STIs, if indicated ● Provide available test results

24-hr/48-hr/72-hr Post Last Dose – Visit 7		
Component	Procedures	
Laboratory	Urine	
 ○ Pregnancy test ○ Urine dipstick/urinalysis, if indicated
	Blood	
 ○ Plasma for PK ○ HIV, HSV-2*, Syphilis ○ CBC with platelets, Chemistries
	Genital	
 ○ PSA test ○ Gram stain for Nugent score, pH ○ TV, GC, CT testing ○ CVF for PK and PD ○ CVL for soluble markers ○ Vaginal microbiota ○ BXV for IHC ○ BXV for PK ○ BXC for HIV (EVMS only) ○ Saline/KOH wet mount for candidiasis and/or BV, if indicated
	Anorectal	
 ○ RF for PK (if participant agrees)

*HSV-2 results will not be provided to participants

7.3.5 Study Exit Visit (SEV) – Visit 8

Visit 8 should be scheduled 10 days after the participant’s last biopsy at Visit 7. Participants will provide a urine sample for a UPT and undergo HIV testing. Participants will also undergo collection of CVL, blood for PK, CVF for PK, PD, and vaginal microbiota, and (if participant agrees) RF for PK. A subset of participants will also be asked to complete an in-depth interview (IDI) to further explore their experiences using the study product. This visit constitutes the Study Exit Visit (SEV).

Table 8: Study Exit Visit (SEV)

Study Exit Visit (SEV) – Visit 8		
Component	Procedures	
Administrative and Regulatory	
 ● Exit from study ● Provide reimbursement 	
Behavioral/Counseling	
 ● Pre- and post-test HIV counselling, and risk reduction counselling ● IDI (subset) 	
Clinical	
 ● Review/update medical history ● Assess for AE and CM ● Pelvic exam ● Directed physical examination, if indicated ● Vital signs and weight ● Treat or prescribe treatment for RTI/UTI/STIs, if indicated ● Provide available test results 	
Laboratory	Urine	
 ○ Pregnancy test ○ Urine dipstick/urinalysis, if indicated
	Blood	
 ○ HIV ○ Plasma for PK
	Genital	
 ○ PSA test ○ Gram stain for Nugent score, pH ○ CVF for PK and PD ○ CVL for soluble markers ○ Vaginal microbiota ○ TV, GC, CT testing, if indicated ○ Saline/KOH wet mount for candidiasis and/or BV, if indicated
	Anorectal	
 ○ RF for PK (if participant agrees)

7.4 Follow-up Procedures for Participants Who Temporarily Hold or Permanently Discontinue Study Product

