5.2 Inclusion Criteria

Individuals must meet all the following criteria prior to baseline sampling at Visit 2 (Enrollment), unless otherwise specified:

- 1) Aged 18 to 50 years (inclusive) at Screening.
- 2) Assigned female sex at birth.
- 3) Able and willing to provide written informed consent to be screened for and enrolled in MATRIX-001 in one of the study languages (as specified in site SOP).
- 4) General good health (by volunteer history) without any evidence of clinically significant systemic disease (as determined by Investigator of Record [IoR] or designee).
- 5) Has had vaginal sex and has an intact uterus and cervix.
- 6) Has a regular and/or predictable bleeding pattern based on the opinion of the investigator, or is oligomenorrhoeic or amenorrhoeic.
- 7) HIV-uninfected based on testing performed at Screening and Enrollment (per protocol algorithms in Appendix II).
- 8) Negative urine pregnancy test at Screening and Enrollment.

- 9) Protected from pregnancy by an effective contraceptive method as confirmed by site SOP; effective methods include:
 - minimum of 3 months of use of a combined hormonal contraceptive method (except vaginal rings)
 - minimum of 6 months of use of a progestin only contraceptive method or copper IUD
 - Sterilization of participant or partner
 - Correct and consistent condom use (for US site only)
 - Abstinence from penile-vaginal intercourse (for US site only)
- 10) Participants over the age of 21 (inclusive) must have documentation of a Grade 0 Pap smear within the past 3 years prior to Enrollment, per the Female Genital Grading Table for Use in Microbicide Studies Addendum 1 (Dated November 2007) to the DAIDS Table for Grading Adult and Pediatric Adverse Events, Corrected Version 2.1, July 2017, or Grade 1 Pap smear at Screening with no treatment required.
- 11) Normal cervicovaginal mucosa (as defined in MATRIX-001 Study Specific Procedures [SSP] manual).
- 12) Willing and able to comply with protocol requirements, including abstaining from vaginal activity and product use at specified times (see Section 6.7.2).
- 13) Per participant report, if in a relationship, must be in a mutually monogamous relationship with a partner who is not known to be HIV positive or to currently have an STI.

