15 APPENDICES

APPENDIX I: SCHEDULE OF STUDY VISITS AND EVALUATIONS

[figure not shown]
	Screening Visit 1	Enrollment Visit 2	Random- ization Visit 3	Post 3 rd Dose Visit 4	4 th & 5 th Dose Visits 5-6	Post Last Dose Visits 7a,b,c	SEV Visit 8	
			10-14 days post V2	3 days post V3	V5 is 10- 14 days post V4	Participants attend only 1 timepoint 11, 12 or 13 days post V6	10 days post V7	
ADMINISTRATIVE AND REGULATORY								
Informed consent process	X							
Assign a unique PTID	X							
Assess/confirm eligibility	X	X						
Collect/review/update locator information	X	X	X	X	X	X	X	
Provide reimbursement	X	X	X	X	X	X	X	
Schedule next visit/contact	*	*	X	X	X	X		
Randomization (1:1) study product (after HIV and pregnancy tests)			X					
Randomization (1:1:1) PK tail sampling (after HIV and pregnancy tests)			X					
BEHAVIORAL/COUNSELING								
Protocol adherence counseling	X	X	X	X	X	X		
HIV pre and post/ risk reduction counselling	X	X	X			X	X	
Demographic information	X							
Behavioral questionnaire		X				X		
Product use questionnaire		X	X	X		X		
IDI (subset)							X	
CLINICAL								
Physical exam (directed after Screening)	X	*	*	*	*	*	*	
Vital signs and weight		X	X	X	X	X	X	
Collect/review/update medical and menstrual history	X	X	X	X	X	X	X	
Pelvic exam (bimanual exam at Screening)	X	X	X	X	X	X	X	
Assess AEs			X	X	X	X	X	
Assess CMs	X	X	X	X	X	X	X	
LABORATORY								
URINE	Pregnancy test	X	X	X	*	*	X	X
	Urine dipstick/ urinalysis	X	*	*	*	*	*	*

		Screening Visit 1	Enrollment Visit 2	Random- ization Visit 3	Post 3 rd Dose Visit 4	4 th & 5 th Dose Visits 5-6	Post Last Dose Visits 7a,b,c	SEV Visit 8
				10-14 days post V2	3 days post V3	V5 is 10- 14 days post V4	Participants attend only 1 timepoint 11, 12 or 13 days post V6	10 days post V7
BLOOD	HIV test	X	X	X			X	X
	HBsAg	X						
	CBC with platelets, Chemistries	X					X	
	HSV-2, Syphilis	X					X	
	Plasma for archive		X					
	PK (Plasma): TAF, TFV, EVG				X	X	X	X
PELVIC	GC, CT, TV testing	X	*	*	*	*	X	*
	Saline/KOH wet mount for candidiasis &/or BV	*	*	*	*	*	*	*
	PSA (semen marker)		X	X	X	X	X	X
	Pap smear	*						
	Gram stain for Nugent score, Vaginal pH		X	X	X	X	X	X
	Vaginal microbiota (16S RNA microbiome)			X	X	X	X	X
	CVF for TAF, TFV, EVG PK levels			X	X	X	X	X
	CVF for Anti-HSV2, Anti-HIV		X	X	X	X	X	X
	CVL (secreted soluble markers)		X	X	X	X	X	X
	BXV for PK – TAF, TFV, EVG, TFV-DP				X		X	
	BXV for IHC		X				X	
	BXC for HIV (EVMS only)		X		X		X	
REC TAL	RF for TAF, TFV, EVG PK levels (if participant agrees)			X	X	X	X	X

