STUDY PRODUCT SUPPLY								
	Study product self-insertion in clinic			X		X		
	Dispense doses for home use			X		X (Visit 6 only)		

X Required

* If indicated and/or per local standard of care

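### Minor, optional safeguard: require a urine pregnancy test at Visit 5, where dosing restarts and 7 of the 10 inserts begin

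*Protocol*

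**What the plan says.** A urine pregnancy test is required at Visits 1, 2, 3, 7 and 8. Entry depends on "Negative urine pregnancy test at Screening and Enrollment" (section 5.2, criterion 8), and section 7.2.2 makes a further negative result a condition of randomization at Visit 3, before dose 1. At Visits 4, 5 and 6 (section 7.3, Tables 4-6) the entry becomes "Pregnancy test, if indicated". Appendix I agrees: the pregnancy row carries an asterisk at Visit 4 and in the shared column "4 th & 5 th Dose Visits 5-6", and the asterisk means "If indicated and/or per local standard of care". Section 7.4.2 gives the same rule.

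Three other provisions bear on the point:
- Criterion 6 of section 5.2 admits a woman who "Has a regular and/or predictable bleeding pattern based on the opinion of the investigator, or is oligomenorrhoeic or amenorrhoeic".
- Menses-based timing is limited to cycling women: "Visit 3 will be scheduled shortly after menstrual flow ceases for cycling participants" (section 7.2.2), with a parallel rule for Visit 5 in section 7.3.2.
- Section 6.7.2 bars intercourse from 48 hours before Enrollment, and then "during daily dosing phase and approximately 48 hours before and 10 days after CVT biopsy collections".

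**The concern.** Pregnancy is a mandatory reason for permanent product discontinuation (section 9.3), and participants are told that effects on a human fetus are unknown (section 13.7.1). The protocol asks for a negative test before the first three inserts but not before the remaining seven. On the planned calendar, the next required test comes too late to prevent any exposure.

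For a cycling woman, a missed period can prompt a test, and Visits 3 and 5 follow menses. An oligo- or amenorrhoeic woman has neither protection. If she conceives just before Visit 3, that visit's test is too early to show it, and she may complete all 10 inserts before the next required test. Finding the pregnancy at Visit 5 would avoid 7 inserts: 7 x 20 = 140 mg TAF and 7 x 16 = 112 mg EVG over 12 days.

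**Working it through.** **1. Calendar (Visit 3 and dose 1 = day 0).** Inputs are from sections 6.1, 7.2.2 and 7.3.1-7.3.4.
- Doses 1-3: days 0, 1, 2. Visit 4: day 3.
- Visit 5 = 3 + (10 to 14) = day 13-17, so dose 3 to dose 4 is 11-15 days.
- Doses 4-10 fall at Visit 5 + 0, 2, ..., 12, so dose 10 is on day 25-29.
- Visit 7 = Visit 5 + 2 + (11 to 13) = day 26-32.

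This reproduces the plan's own figures: 10 doses, dose 5 at Visit 6, and Visit 7 at 24, 48 or 72 hours after dose 10. All 10 doses lie between two required tests 26-32 days apart.

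**2. Days on which intercourse is permitted (section 6.7.2).** The alternate-day phase is read as not covered by the ban on the daily dosing phase.
- Before Visit 3: (10 to 14) - 10 = 0-4 days.
- Before Visit 5: (10 to 14) - 10 = 0-4 days.
- Visit 5 to 48 hours before Visit 7: (13 to 15) - 2 = 11-13 days.

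**3. Detectability.** Assume that a urine test is usually positive from about 12 days after conception (range 10-14), and take the day of intercourse as the day of conception. A conception in the window before Visit 3 is:
- 0-4 days old at Visit 3, so not detectable;
- 13 to (17 + 4) = 13-21 days old at Visit 5, so usually detectable;
- 26 to (32 + 4) = 26-36 days old at Visit 7, after dose 10.

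With a 14-day threshold, the part of the window that Visit 5 is sure to detect shrinks from 0-4 days to 1-4 days before Visit 3. The 4-day upper values below do not change.

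**4. Expected conceptions that a Visit 5 test could find.** The formula is n x (1 - (1 - r)^(d/365)), with n non-cycling women, annual pregnancy risk r and d permitted days. The protocol gives neither n nor r, so both are assumptions.

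| n | r | d | Expected, all | On active (half) |
|---|---|---|---|---|
| 30 | 1% | 0 | 0 | 0 |
| 30 | 1% | 4 | 0.0033 | 0.0017 |
| 15 | 1% | 4 | 0.0017 | 0.0008 |
| 45 | 6% | 4 | 0.031 | 0.015 |

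**5. What the test would still miss.** For n = 30 and r = 1%, the 11-13 permitted days after Visit 5 give 0.0091-0.0107, about three times the 0.0033 that the test could find. The 0-4 days just before Visit 5 are also missed. The catchable share of permitted days is at most 4/(4 + 0 + 11) = 27%. With every window at its longest it is 4/(4 + 4 + 13) = 19%, and with Visit 3 at day 10 it is zero.

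**6. After the change.** The longest planned gap between required tests from Visit 3 to Visit 7 falls from 26-32 days to 13-17 days (Visit 3 to Visit 5), followed by 13-15 days (Visit 5 to Visit 7).

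**The case against.** The strongest case against is that nothing here is wrong. Tables 4-6, Appendix I and section 7.4.2 all say the same thing, so testing when indicated looks like a deliberate choice. A reader might infer a contradiction with the entry criterion or with section 7.2.2. The documents do not support that, because those rules govern enrollment and randomization only. This objection stands.

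The yield is also tiny and rests on assumed inputs. Non-cycling women need not wait for menses, so they can attend Visit 3 at day 10, which leaves no permitted days at all. Most at-risk days fall where a Visit 5 test cannot help, and doses 1-3 have been given in any case. This too stands.

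Other safeguards exist. Effective contraception is required, with condoms or abstinence accepted only at the US site. Visit 5 already includes menstrual history, a pelvic examination before dosing and a PSA test, and participants are encouraged to report signs of pregnancy (section 9.5). Any of these may prompt a test. Appendix I allows testing under local standard of care, and the SSP Manual, which was not available, may define when a test is indicated. It would therefore be wrong to infer that no pregnancy check happens between dose 1 and dose 10. What is missing is a required one.

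A reader might also infer a known fetal hazard. Section 2.3.8 describes reassuring oral animal studies and limited human data without a significant difference in major birth defects, although it calls the registry data insufficient. Section 2.5.1 reports low plasma exposure after a single vaginal dose. The concern is precautionary.

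Finally, a stand-alone amendment needs ethics and, where applicable, regulatory approval in three countries (section 13.1). That is out of proportion to this point, which is why the fix should wait for another amendment.

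**Conclusion.** The point holds as a minor, optional safeguard at the lowest priority. The schedule is internally consistent. It nevertheless restarts dosing at Visit 5, with 7 of 10 inserts to come, without the negative test it demands before dose 1, and no test is required again until after dose 10. The gap mainly affects oligo- or amenorrhoeic women.

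The expected yield is about 0-0.003 conceptions in the base case (30 non-cycling women, 1% annual risk) and about 0.03 at the high end of the range (45 women, 6%), with half on active product. These figures also rest on adherence to the abstinence rules and on the assumed detection threshold. They do not support any claim that fetal exposure is likely in this trial. Sample size, power and the safety comparison are unaffected. The change is worth making only because it costs so little.

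**What to change.** In Table 5 and section 7.3.2, make the Visit 5 urine pregnancy test required, with a negative result before the fourth insert. A minimum version requires it only for women with no menses since Visit 2. In the pregnancy row of Appendix I, write 'X (Visit 5 only)' in the shared Visits 5-6 column, following the format already used there for dispensing at Visit 6. Visits 4 and 6 can stay as they are. Align the consent form if it lists tests by visit.

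The cost is about 60 urine strips, or about 30 in the minimum version on the assumption above, at an existing visit where the test is already listed. A false positive would delay that woman's fourth dose. Bundle the edit with the next amendment.
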